### **6.5.2. Study conduct and patient disposition**

The following analyses will be performed based on the FAS overall and separately by treatment arm.

#### **6.5.2.1. Patient disposition**

The percentages below will be calculated based on the number of patients in the FAS in each treatment arm.

- Total number of patients screened overall;
- Number of patients who discontinued from the study prior to randomization overall and by the main reason for discontinuation;
- Number and percentage of randomized patients in each of the analysis sets defined in Section 4;

- Number and percentage of randomized patients with study drug ongoing during the Lead-in Phase;
- Number and percentage of randomized patients who completed or discontinued study drug overall and by the main reason for discontinuation of study drug during the Lead-in Phase;
- Number and percentage of randomized patients who entered CRT Phase;
- Number and percentage of randomized patients with study drug ongoing (separately for each study drug) during the CRT Phase;
- Number and percentage of randomized patients who completed or discontinued study drug overall and by the main reason for discontinuation of study drug (separately for each study drug) during the CRT Phase;
- Number and percentage of randomized patients with at least one study drug ongoing during the CRT Phase;
- Number and percentage of randomized patients who completed or discontinued all study drugs, discontinued at least one study drug, and completed all study drugs during the CRT Phase;
- Number and percentage of randomized patients who entered the Maintenance Phase;
- Number and percentage of randomized patients with study drug ongoing during the Maintenance Phase;
- Number and percentage of randomized patients who completed or discontinued study drug overall and by the main reason for discontinuation of study drug during the Maintenance Phase;
- Number and percentage of patients who entered follow-up;
- Number and percentage of patients who completed or discontinued follow-up overall and by the main reason for discontinuation;
- Number and percentage of patients who entered long-term follow-up;
- Number and percentage of patients who discontinued long-term follow-up overall and by the main reason for discontinuation.

The results of the randomization algorithm (according to IRT) will be summarized as follows:

- Number and percentage of randomized patients overall, by region (Europe, EEA (required by EudraCT), North America, Latin America, Asia, Australasia, Middle East, Africa), by country within region;
- Number and percentage of randomized patients by center;
- Number and percentage of randomized patients by randomization strata (IRT);
- Number and percentage of randomized patients by randomization strata (eCRF);
- Cross tabulation: stratum by IRT vs. stratum by eCRF;

- Cross tabulation: patients randomized (Arm A/Arm B/none) vs. patients treated (Arm A/Arm B/none).

#### **6.5.2.2. Protocol deviations**

All protocol violations that impact the safety of the patients and/or the conduct of the study and/or its evaluation will be reported. These include:

- Patients who are dosed on the study despite not satisfying the inclusion criteria;
- Patients who develop withdrawal criteria whilst on the study but are not withdrawn;
- Patients who receive the wrong treatment or an incorrect dose;
- Patients who receive an excluded concomitant medication;
- Deviations from GCP.

The identification of these and other CSR-reportable deviations will be based on the inclusion/exclusion criteria or other criteria presented in the protocol.

#### **6.5.3. Study treatment compliance and exposure**

The following analyses will be based on the safety analysis set by treatment arm.

The derivations below are provided for the following:

- Avelumab or matching placebo administered as a 1-hour IV infusion at a dose of 10 mg/kg
  - on Day 1 of the Lead-in Phase (1 week prior to the start of the CRT Phase), and
  - on Days 8, 25, and 39 during the CRT Phase, and
  - once every 2 weeks in 4-week cycles for 12 months (52 weeks) during the Maintenance Phase.
- Cisplatin 100 mg/m^2 administered in 500 mL normal saline over a 60 – 120 minute infusion with an additional 1 to 1.5 L of fluid give post-hydration, on Days 1, 22, 43 during the CRT Phase
- IMRT administered 70 Gy/35 fractions/7weeks, 1 fraction/day, 5 fractions/week)for 7 weeks during the CRT Phase.

Analysis of exposure for avelumab (or matching placebo) and cisplatin will be based on the calculated actual dose levels:

- Avelumab – total dose / weight
- Cisplatin - total dose/m^2

Analysis of exposure for IMRT will be based on the total dose.

### 6.5.3.1. Exposure to avelumab or matching placebo

Exposure to avelumab or matching placebo will be summarized by treatment phase (Lead-in, CRT, Maintenance). In what follows, references to avelumab are meant to apply also to matching placebo.

For Cycle X during the Maintenance Phase, actual cycle start date for each patient is

- the earliest start date of dosing in the Cycle X Day 1 visit eCRF exposure page, if the patient received study treatment on that visit (ie, avelumab dose>0 at that visit)
- the first day of assessments in the Cycle X Day 1 visit, if the patient did not receive study treatment on that visit (ie, avelumab dose=0 at that visit).

Actual cycle end date for each patient is,

- for all cycles X except the last cycle, actual cycle end date = actual cycle (X+1) start date – 1 day;
- for the last cycle, actual cycle end date = actual cycle start date + 28 days – 1 day

**Cycle duration** (weeks) = (actual cycle end date – actual cycle start date + 1)/7

The dose level for avelumab is calculated as actual dose administered/weight (mg/kg). The last available weight of the patient on or prior to the day of dosing will be used.

#### Lead-in Phase

One dose of avelumab is planned to be administered in the Lead-in Phase, the number and percentage of patients who receive the dose will be summarized.

#### CRT Phase

During the CRT Phase, three doses of avelumab are planned to be administered (on Days 8, 25, and 39 of CRT Phase) with a minimum of 14 days required to separate consecutive doses of avelumab or matching-placebo.

**Intended duration of avelumab treatment** in CRT Phase (days) = ((39+14-1)-8+1) = 45

**Duration of exposure to avelumab** in the CRT Phase (days) =

(last dose date of avelumab – first dose date of avelumab + 14)

**Cumulative avelumab dose** (mg/kg) is the sum of the actual doses of avelumab received in the CRT Phase.

**Actual Dose Intensity (DI)** for avelumab in the CRT Phase =

[cumulative dose in the CRT Phase (mg/kg)]/[intended duration of avelumab treatment in CRT Phase (days)/45] (mg/kg/45 days)

**Relative Dose Intensity (RDI)** for avelumab in the CRT Phase is calculated as follows:

- Intended DI (mg/kg/45 days) = 30 (mg/kg/45 days)
- $RDI (\%) = 100 \times [\text{actual DI}] / [\text{intended DI}] = 100 \times \text{actual DI} / 30.$

The summary of treatment exposure and compliance for avelumab in the CRT Phase will include the following information:

- Duration of exposure to avelumab (days);
- Total number of infusions received;
- Cumulative dose (mg/kg);
- Actual DI (mg/kg/45 days);
- RDI (%).

### **Maintenance Phase**

Each cycle for avelumab during the Maintenance Phase is defined by a 4-week period. The dose intensity (DI) and the relative dose intensity (RDI) for avelumab during the Maintenance Phase will be calculated for each patient across all cycles.

**Intended duration of avelumab treatment** in the Maintenance Phase (weeks) =  
(end date – date of first dose of study drug + 1) / 7,

where end date = start date of last cycle with non-zero dose of study drug + 28 – 1

**Duration of exposure to avelumab** in the Maintenance Phase (weeks) =  
(last dose date of avelumab – first dose date of avelumab + 14) / 7

**Cumulative dose** (mg/kg) is the sum of the actual doses of avelumab received during the Maintenance Phase.

**Actual DI** for avelumab in the Maintenance Phase

- Overall actual DI (mg/kg/4-week cycle) = [overall cumulative dose (mg/kg)] / [intended duration of treatment with avelumab (weeks) / 4].

**RDI** for avelumab in the Maintenance Phase

- Intended DI (mg/kg/4-week cycle) = [intended cumulative dose per cycle] / [intended number of 4-weeks in a cycle] = [20 (mg/kg)] / [1 (4-week cycle)] = 20 (mg/kg/4-week cycle)
- Overall RDI (%) =  $100 \times [\text{overall actual DI}] / [\text{intended DI}] = 100 \times [\text{overall actual DI}] / [20 (\text{mg/kg/4-week cycle})]$

The summary of treatment exposure and compliance for avelumab during the Maintenance Phase will include the following information:

- Duration of exposure to avelumab (weeks);
- Total number of infusions received;
- Cumulative dose (mg/kg);
- Actual DI (mg/kg/cycle);
- RDI (%).

#### **Duration of exposure to avelumab across all treatment phases**

**Duration of exposure to avelumab** (weeks) = (last dose date of avelumab – first dose date of avelumab + 14) / 7

**Total number of avelumab infusions** received overall is the sum of the total number of infusions received in each treatment phase.

#### **6.5.3.2. Exposure to Cisplatin**

Cisplatin is to be administered only in the CRT Phase. Three doses of cisplatin (100 mg/m^2) are planned to be administered on Days 1, 22, and 43 of the CRT Phase.

**Intended duration of cisplatin treatment** in CRT Phase (weeks) = 63/7 = 9 weeks

**Duration of exposure to cisplatin** in the CRT Phase (weeks) =

$$(\text{last dose date of cisplatin} - \text{first dose date of cisplatin} + 21) / 7$$

**Cumulative cisplatin dose** (mg/m^2) is the sum of the actual doses of cisplatin received in the CRT Phase.

**Actual Dose Intensity (DI)** for cisplatin in the CRT Phase =

$$[\text{cumulative dose (mg/m}^2\text{)}] / [\text{intended duration of cisplatin treatment (weeks)} / 9] \text{ (mg/m}^2\text{/9-weeks)}$$

**Relative Dose Intensity (RDI)** for cisplatin in the CRT Phase is calculated as follows:

- Intended DI (mg/m^2/9-weeks) = 300 (mg/m^2/9-weeks)
- RDI (%) = 100 × [actual DI] / [intended DI] = 100 × actual DI / 300.

The summary of treatment exposure and compliance for cisplatin will include the following information:

- Duration of exposure to cisplatin (weeks);

- Total number of doses a received;
- Cumulative dose (mg/m^2);
- Actual DI (mg/m^2/9-weeks);
- RDI (%).

a Per protocol, cisplatin dose can be split over a period of 2 to 4 consecutive days. Therefore, if cisplatin is given consecutively over 2-4 days, this will be viewed as a split dose. Split doses will be summed up and categorized as a single dose.

#### **6.5.3.3. Exposure to IMRT**

IMRT is to be administered only in the CRT Phase. The total dose and duration of IMRT administration will be calculated for each patient during the CRT Phase.

**Duration of IMRT** (days) = number of days IMRT is administered.

**Total dose of IMRT** (Gy) = duration of IMRT (days) × 2.

The number of days IMRT is administered and compliance with IMRT administration (“Appropriate”, “Variation acceptable”, “Deviation unacceptable”) will be assessed by a central vendor for each patient during the CRT Phase.

The summary of treatment exposure and compliance for IMRT will include the following information:

- Duration of IMRT (days);
- Total dose of IMRT (Gy);
- Overall compliance (Appropriate, Variation acceptable, or Deviation unacceptable).

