#### **5.4.1.4. Compliance Criteria**

Treatment breaks must be clearly indicated in the treatment record along with the reason(s) for the treatment break(s). Treatment breaks are highly discouraged; however, if necessary for severe acute toxicity, ideally should not exceed 5 treatment days at a time and 10 treatment days in total. Treatment breaks should be allowed only for resolution of severe acute toxicity and/or for intercurrent illness.

Days that the RT department is closed, RT is not expected to be administered and this is not a treatment break. This includes all statutory holidays in that locale. Over times of multiple, consecutive days of holidays, the site is encouraged but not required to “make up” the RT fractions through BID treatments, at least 6 hours apart, during the shortened treatment week.

It is recognized that over the course of 35 treatment fractions in RT various factors aside from statutory holidays may result in RT not being delivered on a day that otherwise could be a potential RT treatment day. It is expected that sites will attempt to keep the overall RT treatment duration as close to 7 weeks as possible, but inability to deliver the RT fraction to a patient on a given day is not a PD unless >2 consecutive regular treatment days (Mon-Fri) are missed. Sites are encouraged to consider BID treatments, at least 6 hours apart, for making up missed RT fractions to maintain the overall treatment time.

RT delivered to the total dose of 70 Gy is a completed dose, regardless of delays in RT delivery.

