### **5.2.3. Presentation of continuous and qualitative variables**

Continuous variables will be summarized using descriptive statistics ie, number of non-missing values and number of missing values [ie, n (missing)], mean, median, standard deviation (SD), minimum, maximum and first and third quartile (Q1 and Q3).

Qualitative variables will be summarized by frequency counts and percentages. Unless otherwise specified, the calculation of proportions will include the missing category. Therefore, counts of missing observations will be included in the denominator and presented as a separate category.

In case the analysis refers only to certain visits, percentages will be based on the number of patients still present in the study at that visit, unless otherwise specified.

Confidence intervals (CIs) may also be reported as noted in subsequent sections.

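### Total IMRT dose is derived as treatment days × 2 Gy, so each day with two fractions, which the protocol allows and encourages for making up missed treatment, is under-counted by 2 Gy

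*SAP*

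**What the plan says.** SAP 6.5.3.3 (Exposure to IMRT) defines duration as the "number of days IMRT is administered" and total dose in Gy as "duration of IMRT (days) × 2". A central vendor supplies the day count and a three-level compliance category. SAP 6.5.3 adds: "Analysis of exposure for IMRT will be based on the total dose".

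Protocol Section 5 plans 70 Gy in 35 fractions over 7 weeks, one fraction per day on five days a week. Protocol 5.4.1.4 then allows for missed days in two settings:

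- Where several holidays fall together, sites are encouraged, but not obliged, to make up the "RT fractions through BID treatments, at least 6 hours apart, during the shortened treatment week".
- For other missed days: "Sites are encouraged to consider BID treatments, at least 6 hours apart, for making up missed RT fractions to maintain the overall treatment time".

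The same section defines completion by dose: "RT delivered to the total dose of 70 Gy is a completed dose, regardless of delays in RT delivery".

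**The concern.** The multiplier of 2 belongs to a fraction, but the SAP applies it to a day. The two agree only under strict once-daily treatment, and the protocol invites sites to depart from that when fractions are missed. A patient whose site follows that invitation and delivers the full course would be reported as having received less than the full dose.

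As defined, total dose is also just the day count times a constant, so the dose row carries no information beyond the duration row. A patient who stops after 33 daily fractions (66 Gy) and a patient who receives all 35 fractions in 33 days (70 Gy) both appear as 66 Gy.

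At stake is the accuracy of the one radiotherapy dose variable the trial will report. No efficacy result depends on it.

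**Working it through.** **Inputs**

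- Planned course: 70 Gy in 35 fractions, 7 weeks × 5 days (Protocol Section 5; SAP 6.5.3).
- Dose rule: days on which IMRT was given × 2 (SAP 6.5.3.3).
- Two fractions on one day are permitted as make-up (Protocol 5.4.1.4).
- About 640 / 2 = 320 patients per arm (SAP 2.2).
- The share of patients with two-fraction days, and the number of such days, are not given. The values below are assumptions.

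**Reproducing the planned dose.** Dose per fraction = 70 / 35 = 2 Gy. Once-daily treatment takes 7 × 5 = 35 days, and 35 × 2 = 70 Gy, so the rule is exact. It is also exact when missed fractions are given on added days, because there are still 35 treatment days.

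**Effect in one patient.** Let b be the number of two-fraction days in a complete 35-fraction course. Treatment days = 35 − b, delivered dose = 35 × 2 = 70 Gy, and SAP dose = 2 × (35 − b) = 70 − 2b.

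| b | Treatment days | Delivered (Gy) | SAP total (Gy) | Shortfall |
|---|---|---|---|---|
| 0 | 35 | 70 | 70 | 0 |
| 1 | 34 | 70 | 68 | 2 Gy (2.9%) |
| 2 | 33 | 70 | 66 | 4 Gy (5.7%) |
| 3 | 32 | 70 | 64 | 6 Gy (8.6%) |
| 5 | 30 | 70 | 60 | 10 Gy (14.3%) |

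The last row is an illustrative extreme.

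**Effect on the arm mean.** If a share p of the arm has b such days each, the mean is understated by 2 × p × b Gy.

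| p | b = 1 | b = 2 | b = 3 |
|---|---|---|---|
| 0% | 0 | 0 | 0 |
| 2% | 0.04 | 0.08 | 0.12 |
| 10% | 0.2 | 0.4 | 0.6 |
| 30% | 0.6 | 1.2 | 1.8 |

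**Effect on the other summary statistics.** SAP 5.2.3 also calls for the minimum, quartiles and median. Suppose all 320 patients in an arm received 70 Gy and those affected had b = 1.

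- Minimum: wrong as soon as one patient has a two-fraction day.
- First quartile: 70 at p = 24%, 68 at p = 26%.
- Median: still 70 at p = 30%, 69 at p = 50%.

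**Does anything else in the SAP correct it?** No. The dose-reduction and dose-delay summaries (SAP 6.5.3.4 and 6.5.3.5) cover avelumab or placebo and cisplatin only. The vendor's compliance category is not a dose.

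**The case against.** The best case for leaving the text alone is that the consequence is small. The table is descriptive and the same rule applies to both arms. The per-protocol criteria (SAP 4.3.1) do not use IMRT dose, and neither does any test or stopping rule. Two fractions on a day are the exception to a once-daily plan, and the documents give no frequency, so the arm-level error could be close to zero. Readers also get the vendor's compliance rating beside the dose. All of this stands and limits the importance of the point. It does not make the rule right for the patients it misstates.

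A second argument is that the vendor may in practice count fractions, in which case no dose would be wrong. The documents cannot settle this. The SAP says days, though, both in the definition and in describing what the vendor provides. If fractions are meant, the wording needs correcting and the duration row is mislabelled.

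Third, Protocol 1.2.2 reports a median IMRT dose of 70 Gy (range 40.0 to 70.0) among early patients who completed IMRT. It does not say how that dose was derived. A correct median would in any case be compatible with the error, since the median moves only when about half the patients are affected.

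A comparison with cisplatin helps only a little. For doses given over several days the SAP states "Split doses will be summed up and categorized as a single dose", so it does adapt a count to a permitted variation. That note concerns the number of doses; cumulative cisplatin dose is already a sum of actual doses.

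**Conclusion.** The concern holds. As written, the SAP understates total IMRT dose by exactly 2 Gy for every day on which two 2 Gy fractions are given. The error always runs towards apparent under-dosing, and it places patients who met the protocol's 70 Gy completion mark below it.

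The per-patient figure rests only on 2 Gy per fraction and on the SAP's day count meaning days. The arm-level figure of 0.2 to 1.8 Gy rests on an assumed 10% to 30% of patients with 1 to 3 such days each, and falls towards zero with rarer use. A difference between arms is possible but hypothetical. The effect is confined to the IMRT exposure summary and leaves PFS, OS, alpha, power and the analysis sets unchanged. The point merits correction because the reported dose would be wrong under a protocol-permitted practice and the remedy is simple.

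**What to change.** In SAP 6.5.3.3, define total dose as the number of fractions delivered × dose per fraction, or take the recorded delivered dose from the IMRT data. Keep the number of treatment days as a separate duration variable. Elapsed time from first to last fraction could be added but is not needed for the correction.

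The cost is a few words and one derivation. SAP Section 2 already lists IMRT data among the non-CRF sources. The documents do not say whether that transfer holds a fraction count or a delivered dose, so this must be confirmed with the central vendor, together with what its day count represents. The radiotherapy schedule is not affected.

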#### **6.5.3.4. Dose reductions**

Applicable to avelumab, matching placebo and cisplatin.

For avelumab or matching placebo, dose reduction is defined as actual non-zero dose < 90% of the planned dose. The number and percentage of patients with at least one dose reduction as well as a breakdown of the number of dose reductions (1, 2, 3, ≥4) will be summarized overall and by treatment phase (Lead-in, CRT, Maintenance).

For cisplatin, a dose reduction is defined as a reduction to dose level -1 (75 mg/m^2) or dose level -2 (50 mg/m^2). The number and percentage of patients with at least one one-dose level reduction, and with at least one two-dose level reduction as well as a breakdown of the number of dose reductions will be summarized.

### 6.5.3.5. Dose Delays

Applicable to avelumab, matching placebo, and cisplatin.

Dose Delay is the difference between the actual time between two consecutive non-zero doses and the planned time between the same two consecutive non-zero doses.

Dose Delay for Dose x (days) = Date of Dose x – Date of Dose (x-1) – Planned days between two consecutive doses.

- Lead-in Phase: not applicable
- CRT Phase:
  - cisplatin: the number of planned days between two consecutive doses is 21 days;
  - avelumab or matching placebo: not applicable (note that the protocol mandates a minimum interval between doses but does not establish a fixed number of days between two consecutive doses);
- Maintenance Phase (avelumab or matching placebo only): the number of planned days between two consecutive doses is 14 days.

Dose delays will be grouped into the following categories:

- No delay;
- CRT Phase: 1-2 days delay; 3-6 days delay;
- Maintenance Phase: 1-3 days delay; 4-6 days delay;
- 7 or more days delay.

In the CRT Phase, no delay and 1-2 days delay will also be summarized together, and in the Maintenance Phase no delay and 1-3 days delay will also be summarized together.

The number and percentage of patients with delayed study drug administration and maximum length of delay, ie, the worst case of delay if patients have multiple dose delays will be summarized

- for avelumab or matching placebo: in the Maintenance Phase;
- for cisplatin: in the CRT Phase.

### 6.5.3.6. Infusion rate reductions

Applicable to avelumab, matching placebo and cisplatin.

The number and percentage of patients with at least one infusion rate reduction of  $\geq 50\%$  compared to the first infusion rate reported in the eCRF as well as the frequency of patients with 1, 2, 3, or  $\geq 4$  infusion rate reductions of  $\geq 50\%$  will be summarized

- for avelumab or matching placebo: overall and by treatment phase (Lead-in, CRT, Maintenance);

- for cisplatin: in the CRT Phase.

#### 6.5.3.7. Infusion interruptions

Applicable to avelumab, matching placebo and cisplatin.

An infusion interruption is defined as an infusion that is stopped and re-started on the same day (ie, for a visit more than one infusion start time and infusion end time are recorded).

The number and percentage of patients with at least one infusion interruption as well as the frequency of patients with 1, 2, 3, or  $\geq 4$  infusion interruptions will be summarized

- for avelumab or matching placebo: overall and by treatment phase (Lead-in, CRT, Maintenance);
- for cisplatin: in the CRT Phase.

